8.0 Consent Process

Caregivers and Adolescents

If the adolescent and caregiver meet eligibility requirements and the caregiver and youth are interested, the research assistant (RA) will conduct a consent appointment by phone, either by continuing the eligibility call or scheduling another time to contact the caregiver and youth. The consent appointment may also take place via Microsoft Teams. During the consent session with both the caregiver and youth present, the RA will explain the purpose of the research, the nature of the study, potential benefits and risks, the voluntary nature of participation, and the data collection procedures to caregivers and the youth. Caregivers will provide consent and youth will provide assent by signing the informed consent document if they both agree to participation in the study. The RA conducting the consent session will document the consent process on a study participant contact log.

Youth who turn 18 during the course of the study will be re-consented on the Young Adult consent document.

Families will be sent a link to the consent form by email and will sign the form electronically via REDCap. Upon completion the REDCap platform will retain a signed copy of the consent form. A signed copy will be emailed to the family for their records.

Changes in Primary Caregiver

In the event that the youth experiences a change in his/her primary caregiver during the course of the study, a RA will screen the new caregiver to determine caregiver eligibility. If the caregiver is eligible and interested in participating in the study, a new consent form will be signed by the youth and the new caregiver. If the new caregiver is not eligible and/or not interested in participating in the study but agrees for the youth to continue participation, we will collect signatures from the caregiver and youth on a new consent form.

Community Health Workers:

Community Health Workers (CHWs) will be asked to participate in the study by participating in the focus group. This data will be used to help improve the DWN-FIT Families intervention and application in the future. We are requesting a waiver of consent for this aspect of the study. [name], a non-MUSC project investigator, who is not the CHWs' supervisor will describe the purpose of the study, focus group, emphasize the voluntary nature of the information requested, and indicate that the CHW can terminate participation in the focus group or decline to answer any of the assessment questions at any time. Confidentiality of the information they provide will also be emphasized.

Social Support Persons:

We are also requesting a Waiver of Consent for individuals requested to be social support persons for families randomly assigned to the DWN-FIT-SS condition. Social support persons will participate in the focus group and provide encouraging messages to the caregiver and adolescent as they progress through the treatment. The research assistant will schedule a time to meet with the social support person by phone or Microsoft Teams. At the appointment, the research assistant will describe the purpose of the study, focus group, emphasize the voluntary nature of the information requested, and indicate that the participant can terminate participation in the focus group or decline to answer any of the assessment questions at any time. Confidentiality of the information they provide will also be emphasized.

Justification of Waivers of Consent

We are requesting waivers of consent for the CHWs and Social Support Persons. The only data collected from these participants will be demographics data and DWN app feedback in the focus group.

9.0 Study Design / Methods

Study participation will last 3 months. Families who consent to participate will be instructed to download the DWN app and complete a demographics survey. The research assistant will schedule the first session with the CHW and mail the weight scale, yoga mat, resistance bands, and Fitbit Inspire 3s to the family. Families will be randomly assigned to one of two intervention groups: the DWN-FIT or the DWN-FIT_Social Support (SS) group. CHWs will meet with families once a week for 3 months via video chat interface on the DWN-FIT app. The sessions will last approximately 45-minutes to 1 hour and will include: 1) review of SM goals; 2) review of PA steps and calories burned; 3) goal setting based on assessments and learning modules; and 4) review of CBST learning modules using evidence-based steps for skill acquisition (discussion of rationale, modeling of skill, caregiver and AAAO behavioral rehearsal of skill, feedback), and caregiver and AAAO develop implementation plans for between session skills practice.

We will also conduct a focus group with the participants after W12 of the study. These 17 focus groups (16 with participants and support person and 1 with all CHWs) will be guided by the responses to the needs analysis and usability evaluation; however, the questions will be open-ended to encourage discussions to obtain a fuller understanding of their personal experiences using the DWN. We will subsequently transcribe the audio recordings and group the data based on the discussion questions. Then, we will use either an inductive thematic analysis or a bottom-up technique to identify themes or recurring patterns in the responses. Caregivers, AAAOs, Supporters, and CHWs will be compensated \$195.55 for participating in a focus group.

Aim 1: Feasibility Testing. Evaluate the DWN-FIT intervention (delivered by 2 CHWs) with 16 families (AAAO and caregiver, overweight or obese) undergoing treatment for adolescent obesity to determine the degree to which the components of the digital intervention are correlated with adolescent-caregiver engagement in healthy behaviors and adherence to the prescribed treatment. Additionally, we will determine the degree to which SS, as an additional element of DWN-FIT, enhances engagement and retention of families within treatment.

Methods: This aim follows two conditions (DWN-FIT vs DWN-FIT_Social Support [SS]) x 4 time (T0: baseline, T1: 1-month follow-up, T2: 2-month follow-up, and T3: 3-month end of treatment), with random assignment of 16 families (caregivers/AAAO) to one of the two treatment conditions. The proposed 3-month treatment period is too short to assess the feasibility of this digital treatment with respect to weight loss measurements (secondary outcomes), so instead we will assess feasibility of this approach based on the development of healthy behaviors (primary outcomes) that have been shown to lead to sustainable weight loss over time. Primary outcomes will be measured after each session (weekly) through the data recorded by the DWN app. These primary measures consist of the following measurements via the DWN app: step count, PA and PA video views, frequency and consistency of nutrition SM, messaging read and response rates, frequency and consistency of CBST education participation, telehealth session attendance, and CM rewards. In both treatment conditions, we will determine correlation between these measures and our measures of engagement and adherence. We will also determine the effect of semi-automated SS on each of the measures by comparing outcomes from each treatment group (DWN-FIT vs DWN-FIT_SS). Caregiver and AAAO percent

overweight and body-mass index (BMI) will serve as secondary outcome measures and will be collected each week via a provided digital scale. These secondary outcomes will be used to build preliminary data for a future full time-course (6-month or greater) randomized clinical trial (RCT).

Measures: We will measure **engagement** through the delivery of the 9-item Patient Health Engagement (PHE)⁴⁸ survey. The PHE is used to determine the degree to which patients are engaged in their own health and describes the patient's ability to manage their own health. PHE has been validated in other work, but a sample size large enough to meet this threshold is outside the scope of this study. The PHE outcomes gathered here will be used as preliminary data for future studies. The PHE survey will be taken via the DWN app at each time point, T0-T3. We will measure **adherence** through comparing the prescribed tasks against the task completed, raw counts (video views, SM entries, PA participation), by each set of participants. We will explore how SS is correlated with adherence to the prescribed treatment.

Aim 2: Patient Centered Evaluation. Conduct a needs analysis before the intervention, a usability evaluation during the intervention and focus groups with participants after the intervention to determine if DWN met their needs for accessing (participants), delivering (CHWs), and providing support during the treatment.

Needs Analysis: We will develop a pre-survey (at T0 guided by [name]) consisting of a set of qualitative questions that determine the participants' goals and needs related to accessing, delivering, and providing support during the treatment. After completion of the intervention (T3), we will conduct a post-survey to determine if DWN-FIT met their needs and goals. Using responses from these two surveys, we will perform an inductive thematic analysis or a bottom-up technique to identify themes or recurring patterns in participants' responses.

Usability Evaluation: We will deliver a usability assessment via the System Usability Scale (SUS)⁴⁹ assessment that will be delivered to the participants at the midpoint of the intervention; it will focus on the efficiency and effectiveness of accessing, delivering, and providing support during the treatment including such topics such as readability, technology literacy, and interface design.

Construct	Measure / Items	Information / Data Source	When Completed*													
			0	1	2	3	4	5	6	7	8	9	10	11	12	13-16
Eligibility/Screening Criteria																
%Overweight	• Body Mass Index (BMI; height and weight measurements)	Youth & CGs	✓													
Primary Outcome Measure																
% Body Fat	• Bioelectrical impedance analysis (BIA)	Youth & CGs		✓	✓	✓	✓	✓	✓	✓	✓	✓	✓	✓	✓	✓
Secondary Outcome Measure																
Physical Activity (PA)	• Fitbit Inspire 2 accelerometer	Youth & CGs		✓	✓	✓	✓	✓	✓	✓	✓	✓	✓	✓	✓	✓
	• Fitbit data	Youth & CG Fitbit		✓	✓	✓	✓	✓	✓	✓	✓	✓	✓	✓	✓	✓
Self-Monitoring of Dietary Intake	• Food/Beverage Log	Youth & CGs		✓	✓	✓	✓	✓	✓	✓	✓	✓	✓	✓	✓	✓
Clinical Note	• Meeting participants	CHW		✓	✓	✓	✓	✓	✓	✓	✓	✓	✓	✓	✓	✓
	• Meeting Duration	CHW		✓	✓	✓	✓	✓	✓	✓	✓	✓	✓	✓	✓	✓
	• Learning module content review	CHW		✓	✓	✓	✓	✓	✓	✓	✓	✓	✓	✓	✓	✓
	• % body fat	CHW		✓	✓	✓	✓	✓	✓	✓	✓	✓	✓	✓	✓	✓
	• Pregnancy screening question	CHW		✓	✓	✓	✓	✓	✓	✓	✓	✓	✓	✓	✓	✓
	• General notes	CHW		✓	✓	✓	✓	✓	✓	✓	✓	✓	✓	✓	✓	✓
Daily Activity Summary	• Food Log Completion	Youth & CGs	✓	✓	✓	✓	✓	✓	✓	✓	✓	✓	✓	✓	✓	✓
	• Number of Steps Taken	Youth & CGs	✓	✓	✓	✓	✓	✓	✓	✓	✓	✓	✓	✓	✓	✓
	• Number of calories burned	Youth & CGs	✓	✓	✓	✓	✓	✓	✓	✓	✓	✓	✓	✓	✓	✓
	• Time spent on learning modules	Youth & CGs	✓	✓	✓	✓	✓	✓	✓	✓	✓	✓	✓	✓	✓	✓
	• Messaging	Youth & CGs	✓	✓	✓	✓	✓	✓	✓	✓	✓	✓	✓	✓	✓	✓
Patient Engagement	• Patient Health Engagement (PHE) Survey	Youth & CGs		✓				✓				✓				✓
Eligibility	• Pregnancy (asked by CHW)	Youth & CGs		✓	✓	✓	✓	✓	✓	✓	✓	✓	✓	✓	✓	✓
Demographics	• Family Information Form	Youth, CGs, CHWs	✓													
Qualitative Interview (Focus Groups)	• Gather information on experiences with research and treatment procedures	Youth, CGs, CHWs														✓
Other Measures:																
Mid-Treatment Usability Study	System Usability Scale (SUS) Questionnaire	Youth, CGs, CHWs							✓							
Needs Assessment	Application Needs Pre-Assessment	Youth, CGs, CHWs	✓													
	Application Needs Post-Assessment	Youth, CGs, CHWs													✓	

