Aim 1: Feasibility Testing. Evaluate the DWN-FIT intervention (delivered by 2 CHWs) with 16 families (AAAO and caregiver, overweight or obese) undergoing treatment for adolescent obesity to determine the degree to which the DWN mobile app promotes the client's engagement in healthy behaviors, increased access to treatment for rural AA families, and improved treatment retention compared to the baseline (27% - 55% attrition). Additionally, we will determine the degree to which SS, as an additional element of DWN-FIT, enhances engagement and retention of families in the treatment.

Expected Outcome: We anticipate that healthy behaviors (increased step count, PA, nutrition SM, etc.) will be positively correlated with increased measures of engagement. Continuous engagement, we hypothesize, is highly linked to improved health outcomes, such as weight loss, which should also be reflected in measures of adherence. We also expect that SS will have a positive effect on each healthy measure, serving to increase the average step count, PA participation, and SM when compared to the non-SS condition.

Aim 2: User Centered Evaluations. Conduct a needs analysis before the intervention, a usability evaluation during the intervention and participant focus groups after the intervention to determine if the DWN app met their needs related to accessing (participants), delivering (CHWs), and providing support during the treatment.

Expected Outcome: We expect that the responses from the participants' surveys and the resulting themes will indicate that the DWN app met the participants' goals and needs related to accessing, delivering, and providing support during the treatment and was usable, efficient and effective.

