10.0 Data Management

All data will be safeguarded for confidentiality. Families will be assigned an unique identifier (UID) immediately following enrollment into the study. All sources of data will only have reference to the UID number. A file will also be created that links participants to their UID number. This file, consent and assent documents, screening documents, and de-identified data will all be kept in separate, locked file cabinets in the offices of the RAs at the Medical University of South Carolina in the Division of Global and Community Health (MUSC-GCH). Only study research personnel will have access to data that links research data to participant identifiers during the course of the trial.

Data Analysis Strategy

We will utilize a Pearson correlation coefficient (range -1 to 1) to determine the degree of correlation between components of DWN-FIT and engagement and adherence. Each measure will be quantized into a numerical value that can be used to generate the correlation coefficient. To compare the effect of SS on treatment outcomes we will use an independent two-sample t-test ($\alpha = 0.05$) to determine statistical differences between measures such as step count, PA, SM, etc. with respect to treatment condition.

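### Section 9.0 fixes the primary outcome twice: app-recorded behaviours in the Aim 1 text, percent body fat alone in the schedule table

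*Protocol*

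**What the plan says.** **Aim 1 Methods text, Section 9.0.** The three-month period is described as "too short to assess the feasibility of this digital treatment with respect to weight loss measurements (secondary outcomes), so instead we will assess feasibility" through healthy behaviours, which are labelled the primary outcomes. The list begins: "These primary measures consist of the following measurements via the DWN app: step count, PA and PA video views". It continues with nutrition self-monitoring, messaging, participation in the cognitive behavioural skills (CBST) education, telehealth attendance and contingency management (CM) rewards. For adolescent and caregiver, percent "overweight and body-mass index (BMI) will serve as secondary outcome measures and will be collected each week via a provided digital scale".

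**Schedule table, end of Section 9.0.** The primary outcome heading has a single row, percent body fat, measured by "Bioelectrical impedance analysis (BIA"). Under the secondary heading, the first two constructs are physical activity ("Fitbit Inspire 2 accelerometer" and Fitbit data) and self-monitoring of dietary intake. BMI and percent overweight appear only under eligibility and screening, at week 0.

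**Elsewhere.** The expected outcome of Aim 1 in Section 1.0 is that "SS will have a positive effect on each healthy measure, serving to increase the average step count, PA participation, and SM". The Data Analysis Strategy in Section 10.0 uses a two-sample t-test at alpha 0.05 "to determine statistical differences between measures such as step count, PA, SM, etc. with respect to treatment condition". It labels nothing primary or secondary.

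**The concern.** The two places do not differ only in detail. For physical activity and dietary self-monitoring the roles are reversed, and the measure that the table makes primary has no outcome role at all in the Aim 1 text. The table also gives the top position to a body-composition measure in a trial whose own text argues that three months is too short to judge it on weight loss measurements.

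This is a randomised comparison tested at alpha 0.05, and Sections 1.0 and 2.0 say that successful outcomes are to support a larger randomised trial and commercialisation. With two incompatible primary definitions in current text, whichever result turns out favourable could be presented as the one planned in advance, with a page of the protocol to support it.

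**Working it through.** The protocol gives no power, effect size or sample-size derivation for this point, so there is no figure of its own to reproduce. The check compares the passages and counts matches.

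**1. Match the text's primaries to the table.** Read as comma-separated items, the Aim 1 list has seven entries.

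| Primary in the Aim 1 text | Where it stands in the schedule |
|---|---|
| Step count | Daily activity rows, after the secondary heading |
| Physical activity and activity video views | Physical activity: directly under the secondary heading |
| Nutrition self-monitoring | Directly under the secondary heading |
| Messaging read and response rates | Daily activity rows, after the secondary heading |
| CBST education participation | Learning-module rows, after the secondary heading |
| Telehealth attendance | Community health worker (CHW) meeting rows, after the secondary heading |
| CM rewards | No row |

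Under the table's primary heading: 0 of 7. In the other direction, the one row under that heading, percent body fat, is not on the text's list: 0 of 1.

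**2. Compare the secondary outcomes.** The schedule has columns for weeks 0 to 12 (13 columns) plus one for weeks 13–16, so 13 + 1 = 14. Percent overweight and BMI, weekly in the text, are ticked in 1 of 14 (week 0, as screening). Percent body fat is ticked in 13 of 14 (all but week 0).

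**3. Ask whether the data exist for weekly BMI.** Section 3.0 (Self-Monitoring Assessments) has participants weigh themselves and record body fat weekly, so the weight is available. The only height is the one at screening: Section 7.0 has it self-reported in the pre-screen tool and confirmed by phone, while the schedule's week-0 row speaks of height and weight measurements. The protocol does not say which height enters the weekly BMI.

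**4. Look for anything that settles the conflict.** Section 1.0 and the Data Analysis Strategy name step count, physical activity and self-monitoring, which fits the text. Neither mentions body fat. However, the analysis section assigns no hierarchy and leaves its list open-ended, and no statement gives the text precedence over the table.

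**5. Rule out an artefact.** The table headings and rows are legible, and both versions are current text rather than part of an amendment log. The table also names a Fitbit Inspire 2 where Section 3.0 and the opening of Section 9.0 name the Inspire 3. That has no bearing on the outcome hierarchy, but it is a further sign that table and text were not brought into line.

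**The case against.** The best counter-argument is that the ambiguity is lopsided. The Aim 1 text gives a reason for its choice as well as a label, and the Aim 1 statements and expected outcome and the analysis strategy all agree with it. A careful reader would conclude that the table is mislabelled. This is also a feasibility study in 16 families, with seven primary measures, no power claim and no single endpoint that carries alpha. The disputed behaviour and body-fat measures are collected under either reading.

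That the table is the outlier is right, and it determines the direction of the fix. It does not remove the problem, because nothing in the protocol tells a reader to discount the table. A separate statistical analysis plan, if one exists, could not follow both versions.

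Three narrower objections have merit:

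- The secondary heading cannot safely be taken to govern every row below it, since demographics, the pregnancy question and the focus groups follow it too. Only physical activity and dietary self-monitoring are clearly labelled secondary. The count of 0 of 7 does not depend on this.
- CM rewards are computed from goals met and attendance, so the lack of a row is a weak point.
- The height used for BMI is a derivation detail that could be held elsewhere. It is a side issue here.

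**Conclusion.** The concern holds and should be corrected before any outcome data are analysed. Section 9.0 defines the primary outcome in two incompatible ways: 0 of the 7 text primaries are under the table's primary heading, and the table's only primary is absent from the text. The secondary outcomes disagree as well, weekly against 1 of 14 columns. No sample size, power or error rate is affected, because the protocol derives none; what is lost is a single pre-specified hierarchy. The conclusion rests on reading the table headings as they stand and on the absence of any precedence statement. It needs no outside figure.

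**What to change.** 1. In the schedule table, place the app-recorded behaviours listed in the Aim 1 text under the primary outcome heading, and close each outcome block so that demographics, screening questions and notes do not run on beneath it.
2. Remove percent body fat from the primary heading and give it one role in both text and table. Secondary fits the text's reasoning about the short treatment period. No passage currently assigns it that role, so the sponsor has to confirm it.
3. For percent overweight and BMI, either add weekly weight, BMI and percent-overweight rows and state which height is used, or remove these outcomes from the text.
4. Label the outcomes in the Data Analysis Strategy with the same hierarchy, and reconcile the Fitbit model named in the table with the text.

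The cost is protocol wording and a table edit. Weekly weight and body fat are already recorded. Reusing the screening height adds no procedure; re-measuring height would be a new one.

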1.0 Objectives / Specific Aims

Machine and Human Interaction is a digital health company focused on improving patient outcomes through a virtual care platform, the Digital Wellness Nurse (DWN). The DWN uses human-in-the-loop automation, web, and mobile technology to deliver evidence-based interventions that increase a patient population's access and adherence to treatment and their engagement in healthy behaviors. The focus of the DWN for this study, in collaboration with the Medical University of South Carolina (MUSC), is to evaluate its feasibility in delivering key components of FIT Families (HL155793), a multicomponent behavioral intervention designed to treat 12-to-17-year-old African American (AA) adolescents with obesity (AAAO).

The study aims to expand the FIT Families intervention through a digital adaptation that utilizes mobile technology and automation to increase access and adherence. Specifically, the DWN platform will assist AAAOs and their primary caregivers (participants) in understanding, tracking, and completing intervention components; delivering educational content when needed; and collecting information from external sources such as wearables. An analysis of their progression will provide the participants' incentives for adhering to intervention components, for example increasing their participation in self-monitoring (SM) and physical activity (PA). The DWN enables social support (SS) by allowing additional family members or friends to offer messages of encouragement to the participants throughout the treatment. Using our web-based dashboard, community health workers (CHWs) will monitor the progress of their families, meeting with them weekly via video conference within the DWN mobile application.

DWN-FIT will evaluate the feasibility of a digital intervention to expand access and facilitate adherence to family-oriented, evidence-based treatment for AAAOs and their caregivers. Additionally, the realization of DWN-FIT will enable future research and development of evidence-based digital interventions targeting AAAOs. Successful outcomes of the proposed work will provide the evidence needed to support a larger, more comprehensive randomized clinical trial and commercialization of DWN (Phase II).

Specific Aims:

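### Feasibility is the main question of Aim 1, but no primary measure has a level that counts as feasible, neither planned analysis addresses it, and the one retention benchmark is a range without a rule

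*Protocol*

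**What the plan says.** - **Purpose.** Protocol Section 1.0: "DWN-FIT will evaluate the feasibility of a digital intervention to expand access and facilitate adherence". Aim 1 is titled as feasibility testing there and again in Section 9.0.
- **Basis for the judgement.** Section 9.0, Aim 1 Methods: "we will assess feasibility of this approach based on the development of healthy behaviors (primary outcomes". The listed measures include "step count, PA and PA video views, frequency and consistency of nutrition SM, messaging read and response rates", followed by CBST participation, telehealth attendance and CM rewards. No target, minimum change or rule for combining them is given.
- **Use of the result.** Section 1.0: "Successful outcomes of the proposed work will provide the evidence needed to support a larger, more comprehensive randomized clinical trial and commercialization of DWN". Success is not defined.
- **Analyses.** Section 10.0, Data Analysis Strategy, gives two. A Pearson coefficient is used "to determine the degree of correlation between components of DWN-FIT and engagement and adherence", with no cut-off. The other reads: "To compare the effect of SS on treatment outcomes we will use an independent two-sample t-test", at a level of 0.05.
- **Arms.** Section 3.0 gives SS families every DWN-FIT component plus a supporter. Section 5.0 has 16 families, 8 of them in the SS condition.
- **Benchmark.** Aim 1 in Section 1.0 compares retention with a baseline of 27% to 55% attrition. Aim 1 as restated in Section 9.0 drops this comparator and mentions retention only in connection with SS.
- **Schedule table, Section 9.0.** Percent body fat appears as the primary outcome measure; physical activity and dietary self-monitoring appear as secondary.

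**The concern.** The protocol says what feasibility will be judged on but not what result would count as feasible. The analyses it does specify answer other questions. The t-test isolates the increment from SS; whichever way it falls, it is silent on the programme that both arms share. A correlation can be high when every family engages poorly, so it does not measure feasibility either.

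The level that counts as success could therefore be chosen after the data are seen, from seven measures and from either end of the retention range. The result is meant to support a larger randomised trial and commercialisation, so the choice has consequences.

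**Working it through.** The protocol gives 16 families without a power, effect-size or precision calculation, so there is no planned figure to reproduce. The check is whether the one numerical benchmark can serve as a pass mark.

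**Inputs.** From Section 5.0, n = 16 families. From Section 1.0, attrition of 27% to 55%, which is retention of 1 − 0.27 = 73% down to 1 − 0.55 = 45%.

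**Step 1: turn the range into counts.**
- Lenient end: 0.45 × 16 = 7.2, so 8 or more retained beats it.
- Strict end: 0.73 × 16 = 11.68, so 12 or more retained beats it.
- From 8 to 11 retained (attrition 50% to 31%), the same data are an improvement on one end and not on the other. With 7 or fewer (attrition 56% or more), the result fails both.

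**Step 2: how much the choice of end matters.** P(X ≥ k) for X ~ Binomial(16, p). True retention p is not given, so it is assumed and varied.

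| Assumed true retention | P(X ≥ 8): beats lenient end | P(X ≥ 12): beats strict end |
|---|---|---|
| 45% | 0.44 | 0.01 |
| 60% | 0.86 | 0.17 |
| 73% | 0.99 | 0.56 |
| 85% | >0.99 | 0.92 |

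The two readings give very different chances of success except when retention is very high. The first row also shows that beating the lenient end on the point estimate alone is weak evidence: it happens 44% of the time when retention is no better than 45%.

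**Step 3: what a stated rule could do with 16 families.**
- Reference 45% retention: P(X ≥ 11 | 0.45) = 0.0486, so 11/16 or more excludes it at one-sided 0.049. Power is 0.98 if true retention is 85% (assumed).
- Reference 73% retention: P(X ≥ 15 | 0.73) = 0.045, so 15/16 is needed. Power is 0.28 at an assumed 85% and 0.51 at an assumed 90%.
- Exact (Clopper-Pearson) two-sided 95% intervals: 11/16 gives 41% to 89%; 12/16 gives 48% to 93%. The 11/16 rule is one-sided: its two-sided 95% interval still contains 45%, whereas that for 12/16 does not. The plan must say which convention decides.

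**Step 4: primary measures side by side.** The Aim 1 Methods text makes step count, physical activity and self-monitoring primary. The schedule table in the same section makes body fat primary and puts physical activity and self-monitoring under secondary. A pass mark cannot be attached to the primary measures until these agree.

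**The case against.** **The trial already has a numerical comparator for DWN-FIT itself.** This stands in part. A reader might infer that the trial cannot fail, or that the 0.05 level is the only number against which anything is judged. The documents do not support that: 7 or fewer of 16 families retained would miss even the lenient end of the attrition range. But the range carries no rule, retention is not a listed primary measure, and the analysis strategy does not use the comparator.

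**The t-test is not offered as a feasibility test.** This stands. A reader might infer that a non-significant SS comparison would cause a workable programme to be called unsuccessful. Nothing in the protocol uses the test that way, so the low power of 8 against 8 families is a separate matter and does not measure this defect.

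**A small pilot estimates; it does not decide.** Partly stands. Aim 1 speaks of determining degrees, the secondary outcomes are described as preliminary data, and no formal go/no-go step is laid out. No hypothesis test is therefore required. But Section 1.0 ties success to the next trial, so success needs a meaning fixed beforehand.

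**An unseen SAP may supply the criterion.** This is weak. Analysis detail can wait for an SAP, but what counts as success for the headline aim is a design decision. The protocol takes it up in Section 9.0 and names a basis without a level.

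**Conclusion.** The point holds for the listed primary measures: none has a level that counts as feasible, and neither planned analysis addresses the feasibility of DWN-FIT. For retention it holds in a narrower form: a failing result exists at 7 or fewer families, but the outcome is undecided from 8 to 11.

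At an assumed true retention of 60%, choosing the lenient or the strict end moves the chance of reporting improvement from 0.86 to 0.17; over assumed rates from 45% to 73%, the gap stays between about 0.42 and 0.69. These figures assume that retention is counted by family, that families are independent, and that the comparison uses the point estimate. The absence of a level on the other measures does not depend on those assumptions.

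Safety is not affected. The protocol should be changed, because its main question has no checkable answer as written.

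**What to change.** 1. **Reconcile the outcomes.** Make the Aim 1 Methods text and the schedule table in Section 9.0 agree on which measures are primary.
2. **Add a feasibility analysis** to Sections 9.0 and 10.0, covering all 16 randomised families with both arms combined:
   - the proportion retained, with retained defined, reported with its exact 95% interval and judged against one named reference value from Section 1.0. For example, 11/16 or more excludes 45% retention at one-sided 0.049. State whether the one-sided test or the two-sided interval decides;
   - one family-level adherence criterion from app data, such as session attendance together with nutrition self-monitoring, stating whether the adolescent, the caregiver or both must meet it;
   - proceed, modify and stop cut-offs for the move to the larger trial, set by the sponsor before data are seen.
3. **Separate the other analyses.** State in Section 10.0 that the SS t-tests and the correlations are exploratory and play no part in the feasibility decision.

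The cost is a short amendment using data already collected, with no added visits, staff or families. The price is that the trial can then fail its own mark, and that precision is poor: 12/16 gives 48% to 93%. If the sponsor picks 73% retention as the reference, 15/16 is needed at one-sided 0.05, and even a good programme would often miss it.
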